6.4 Compliance with dosing regime

All vaccinations will be administered by the Investigator and recorded in the CRF. The study IMP will be at no time in the possession of the volunteer and compliance will not, therefore, be an issue.

6.5 Pregnancy

Should a volunteer become pregnant during the trial, no further study IMP will be administered. The volunteer will be followed up for clinical safety assessment with their ongoing consent and in addition will be followed until pregnancy outcome is determined. We would not routinely perform venepuncture in a pregnant volunteer unless there is clinical need.

7. CLINICAL PROCEDURES

This section describes the clinical procedures for evaluating study participants and follow-up after administration of study vaccine.

7.1 Schedule of Attendance

All volunteers will have the schedule of clinic attendances and procedures as indicated in the schedules of attendance (Table 2). The total volume of blood to be taken at each visit will vary and can be up to approximately 130 ml. Additional visits or procedures may be performed at the discretion of the investigators, e.g., further medical history and physical examination, blood tests in event of laboratory abnormalities leading to AE, or urine microscopy in the event of positive urinalysis.

2. Schedule of Procedure

2a. Schedule of Procedures of group 1

Visit number	Screen	1	2	3	4	5	6
Study week	Screen	0	1	1	2	4	16
Study day	-42	0	1	7	14¹	28	112²
Visit windows (days)	(≤ -42)	0	-	±3	±3	±3	±7
Informed consent	X						
Confirm eligibility	X	X					
VACCINATION							
ChAdOx1-tHIVconsV1 low dose			X				
COUNSELLING							
HIV Risk Reduction Counselling	X	X					X
HIV Test Counselling	X	X					X
CLINICAL ASSESSMENTS							
HIV-1 Risk Assessment	X						
Comprehensive Medical History	X						
Interim Medical History		X	X	X	X	X	X
General Physical Exam	X	X					
Symptom Directed Physical Exam			X	X		X	X
Weight	X						
Height	X						
Vital signs	X	X ³	X	X		X	X
Cervical & Axillary lymph nodes		X	X	X			
Adverse Events		X	X	X	X	X	X
Serious Adverse Events		X	X	X	X	X	X
Concomitant Medications	X	X	X	X	X	X	X
Local and Systemic Reactogenicity Assessment ¹		X ⁴		X			
LABORATORY PROCEDURES							
HBsAg, HCV Antibodies (5 ml)	X						X
Syphilis serology	X						X
HIV-Ab (5 ml- when HBsAG and HCV Ab are required, no additional blood for HIV-Ab is needed)	X	X					X
HIV-RNA (10 ml)							X
Urinalysis	X						
Routine Haematology (2 ml)	X	X	X	X		X	X
Coagulation screen and fibrinogen (3 ml)	X	X					X
Biochemistry (4 ml)	X	X		X		X	
Pregnancy Test (if applicable)	X	X					X
Blood volume per visit (ml)	21	13	2	6		9	17
Cumulative blood volume (ml)		34	36	42		51	68

¹ Visit D14 will be conducted by phone; participants might need to attend the clinic at discretion of the investigator. If participants attend the clinic, the visit will be recorded as unscheduled visit.

² Early Termination (ET): Procedures to be performed at ET are the same as the week 16 visit procedures.

³ Collect at baseline and at 30 (±5 min) min post vaccination; first participant in each group will have additional observation at 60 min (±5 min)

⁴ Reactogenicity will be collected from Day 0 to Day 7 after each vaccination.

Table 2b. Schedule of procedures of Group 2

Visit number	Screen	1	2	3	4	5	6	7	8	9	10	11
Study Week	Screen	0	1	1	2	4	4	5	6	8	9	20²
Study day	-42	0	1	7	14¹	28	29	35	42	56	84	140
Visit windows (days)	(≤ -42)	0	0	±3	±3	±3	0	±3	±3	±3	±7	±7
Informed consent	X											
Confirm eligibility	X	X										
VACCINATIONS												
ChAdOx1.tHIVconsV1 high dose		X										
MVA.tHIVconsV3 and MVA.tHIVconsV4							X					
COUSSELLING												
HIV Test Counselling	X	X					X					X
CLINICAL ASSESSMENTS												
HIV-1 Risk Assessment	X											
Comprehensive Medical History	X											
Interim Medical History		X	X	X	X	X	X	X	X	X	X	X
General Physical Exam	X	X				X						
Symptom Directed Physical Exam			X	X			X	X	X	X	X	X
Weight	X											
Height	X											
Vital signs	X	X ³	X	X		X ³	X	X	X	X	X	X
Cervical & Axillary lymph nodes		X	X	X		X	X	X				
Adverse Events		X	X	X	X	X	X	X	X	X	X	
Serious Adverse Events		X	X	X	X	X	X	X	X	X	X	X
Concomitant Medications	X	X	X	X	X	X	X	X	X	X		
Local and Systemic Reactogenicity Assessment ¹		X ⁴	X	X		X ⁴	X	X				
LABORATORY PROCEDURES												
HBsAg, HCV Ab (5 ml)	X											X
Syphilis serology	X											X
HIV-Ab (5 ml- when HBsAG and HCV Ab are required, no additional blood for HIV-Ab is needed)	X	X				X						X
HIV-RNA (10 ml)												X
Urinalysis	X											
Routine Haematology (2 ml)	X	X	X	X		X	X	X	X			X
Coagulation screen and fibrinogen(3 ml)	X	X				X				X		
Biochemistry (4 ml)	X	X		X		X		X	X			
Pregnancy Test (if applicable)	X	X				X						X
Faecal samples		X ⁵						X				X
IMMUNOLOGY												
HLA Typing (4 ml)		X										
Fresh ELISpots (20 ml)		X						X				X
PBMC, serum and plasma storage (frozen ELISpot, VIA, ICS, memory) (100 ml)		X						X	X			X
Epitope Mapping (20 ml)										X	X	
Innate response (2.5 ml)		2.5	2.5	2.5		2.5	2.5	2.5			2.5	2.5
Blood volume per visit (ml)	14	140.5	4.5	8.5	-	16.5	4.5	128.5	100	20	22.5	139.5
Cumulative blood volume (ml)	14	154.5	159	167.5	167.5	184	188.5	317	417	437	459.5	599

¹ Visit D14 will be conducted by phone; participants might need to attend the clinic at discretion of the investigator. If participants attend the clinic, the visit will be recorded as unscheduled visit.

² Early Termination (ET): Procedures to be performed at ET are the same as the week 20 visit procedures.

³ Collect at baseline and at 30 (± 5 min) min post vaccination; first participant in each group will have additional observation at 60 min (± 5 min)

⁴ Reactogenicity will be collected from Day 0 to Day 7 after each vaccination.

⁵ Faecal sample should be collected before administration of the first vaccine dose at enrolment

7.2 Observations

Pulse, blood pressure and temperature will be measured at the time-points indicated in the schedule of procedures and may also be measured as part of a physical examination if indicated at other time-points.

7.3 Blood tests and urinalysis

Blood will be drawn for the following laboratory tests and processed at Oxford University Hospitals NHS Foundation Trust using NHS standard procedures:

- **Haematology;** Full Blood Count – 2 ml taken at screening visit, at each vaccination visit and at 1, 7 and 28 days post each vaccination visit
- **Biochemistry;** Sodium, Potassium, Urea, Creatinine, Albumin, Liver Function Tests (ALT, ALP, bilirubin) – 4 ml taken at screening visit, at each vaccination visit, 7 and 28 days post each vaccination visit
- **Coagulation screen and fibrinogen:** Prothrombin time, APTT and fibrinogen – 3 ml taken at screening visit, each vaccination visit and 28 days post each vaccination visit
- **Diagnostic serology:** HBsAg, HCV antibodies, HIV antibodies, Treponemal IgG/IgM \pm RPR – 5 ml taken at screening visit and at the final visit. Other 5 ml samples for HIV antibodies only are taken at each vaccination visit and the final visit
- **HIV-RNA:** this test will be done at the final visit
- **Urinalysis:** Urine will be tested for protein, blood and glucose at screening using a dipstick. . For female volunteers only, urine will be tested for beta-human chorionic gonadotrophin (β -HCG) at screening, immediately prior to vaccination and at the final visit

Additional safety blood tests may be performed if clinically relevant at the discretion of the medically qualified investigators.

At University of Oxford research laboratories (Group 2 only):

- **Exploratory Immunology;** Immunogenicity will be assessed by a variety of immunological assays. This includes T-cell assays including *ex vivo* ELISpot assays for IFN- γ and, depending on the number of cells available, by further exploratory assays including Intracellular cytokine staining. Further exploratory studies may include, but will not be limited to: virus inhibition assay (VIA) to assess ability of CD8 $^{+}$ T-cells to inhibit virus replication after vaccination, epitope mapping to determine specificity, breadth and depth of the T-cell responses to HTI-encoded regions, T-cell lymphoproliferation as measured by CFSE, T-cell and serologic assays may be conducted to assess immunity to MVA and ChAdOx1. Other exploratory immunological assays including cytokine analysis, DNA analysis of genetic polymorphisms potentially relevant to vaccine immunogenicity and gene expression studies amongst others may be performed at the discretion of the Investigators. All initial investigations will be outlined in the study-specific laboratory plan. Explanatory immunology essays may be performed under the OVC Biobank ethical approval.
- **Faeces sample for the study of gut microbiota;** Faeces will be collected using specific containers following the established SOP for stool collection. After checking by the research nurses and evaluation of the Bristol scale, stool containers will be labelled and processed. Two aliquots of faeces will be stored for DNA analysis per time point and two aliquots for RNA analysis will be stored in RNA-later for subsequent microbiota analyses as outlined in the study-specific laboratory plan.

Collaboration with other specialist laboratories in the UK, Europe and outside of Europe for further exploratory tests may occur. This would involve the transfer of serum, faeces or plasma, PBMCs and/or other study samples to these laboratories for analysis, but these would remain anonymised. Informed consent for this will be gained from volunteers.

Immunological assays will be conducted according to local SOPs.

Participants will be informed that there may be leftover samples of their blood and faeces (after all testing for this study is completed). Samples sent to our collaborators outside the UK, will be destroyed after analysis. Participants will be given a separate PIS and consent form for blood and

faecal research samples remaining at the University of Oxford to be stored indefinitely in the Oxford Vaccine Centre Biobank for possible future research (exploratory immunology), including human DNA and RNA analyses to search for correlates of vaccine immunogenicity and efficacy. If a subject elects not to permit this, all of that subject's leftover samples will be discarded after the required period of storage to meet Good Clinical Practice (GCP) and regulatory requirements. All safety samples will be destroyed after analysis, in line with the Human Tissue Act 2004 and will not be stored for future research use.

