- Proportion of volunteers with local and systemic reactogenicity events from Day 0 to Day 6 post vaccination
- Proportion of volunteers with Grade 3 or 4 unsolicited adverse events (AEs) through 28 days post final vaccination
- Proportion of volunteers with vaccine related serious adverse events (SAEs) collected throughout the study period

SECONDARY

- Proportion of vaccine recipients developing HIV-1-specific T-cell responses
- Frequency, breadth and duration of the tHIVconsvX-specific T-cell responses to conserved epitopes measured in IFN- γ ELISpot assay in each vaccine recipient
- Breadth of inhibition of HIV-1 viruses *in vitro*

EXPLORATORY

- Proportions of mono-, bi- and tri-functional tHIVconsvX-specific T-cells in the vaccine recipients
- Shotgun sequencing and metabolomics analyses.

Investigational products

- The ChAdOx1.tHIVconsv1 vaccine utilises non-replicating engineered simian adenovirus vaccine vector ChAdOx1 to deliver a mosaic immunogen tHIVconsv1 derived from functionally conserved regions of HIV-1 proteins.
- Two vaccine components MVA.tHIVconsv3 and MVA.tHIVconsv4 complement each other and will be used as a pair for immunisations. They utilise non-replicating poxvirus MVA delivering bi-valent mosaic

immunogens, either tHIVconsV3 or tHIVconsV4, derived from functionally conserved regions of HIV-1 proteins.

Formulation Suspension (all finished products)

Route of Administration Intramuscularly (IM), into the deltoid region of each arm

Dose per Administration

- 5.0×10^9 vp of ChAdOx1.tHIVconsV1 (C1 low dose half a dose to be administered to each arm)
- 5.0×10^{10} vp of ChAdOx1.tHIVconsV1 (C1 high dose half a dose to be administered to each arm)
- 1.0×10^8 pfu of MVA.tHIVconsV3 (M3) left arm
- 0.9×10^8 pfu of MVA.tHIVconsV4 (M4) right arm

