7.4 Study visits

The study visits and procedures will be undertaken by one of the clinical trials team. The procedures to be included in each visit are documented in the Schedule of Procedures (Table 2). Each visit is assigned a time-point and a window period, within which the visit will be conducted.

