7.4.3 Subsequent visits

On subsequent visits, where specified in the Schedule of Procedures (section 7.1). Site personnel will:

- Review the e-diary and retain the information in the CRF
- Solicit and record local and systemic AEs
- Review and record interim medical history and concomitant medication
- Perform vital signs (pulse, blood pressure, temperature)
- Perform directed physical examination
- Assess the vaccination site
- Collect blood tests and faeces as specified in the Schedule of Procedures

7.4.4 *Final Visit*

The Final Visit or Early Termination Visit procedures will be performed according to the Schedule of Procedures (section 7.1). Site personnel will:

- Review any AEs and concomitant medications
- Perform vital signs (pulse, blood pressure and temperature)
- Perform a directed physical examination
- Assess any local and systemic reactogenicity events
- Collect blood and urine for tests as specified in the Schedule of Procedures
- HIV and STI screen and specific counselling as per Schedule of Procedure
- Perform a pregnancy test in all female volunteers where appropriate

7.4.5 *Unscheduled visits*

Visits/contacts other than those described in the Schedule of Procedures will be classified as unscheduled visits and recorded on a designated CRF. They may occur:

- For administrative reasons
- To review a laboratory investigation from a previous visit
- To review the outcome of an AE
- To conduct a study visit where a volunteer has missed the scheduled study visit window
- For any other reason requested by the volunteer or CI

7.4.6 *HIV testing and sexually transmitted infections (STI) Counselling*

Site personnel will counsel study participants about the implications of having blood tests for HIV, Hepatitis B, Hepatitis C and syphilis.

All volunteers will be assessed for HIV risk at screening, and tested for HIV antibodies as indicated in the Schedule of Procedures or as needed, if medical or social circumstances arise. All volunteers will receive HIV risk reduction counselling and pre- and post-HIV-test counselling, as specified below.

Trained and qualified study personnel will provide HIV counselling and testing at designated study visits as indicated in the Schedule of Procedures. Counselling will be provided in compliance with national guidelines.

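### Table 2b's volume row has no room for the haematology, biochemistry and coagulation that section 7.3 requires at D56 (608 ml itemised, 599 ml stated)

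*Combined protocol and SAP*

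**What the plan says.** Section 7.3 fixes three safety panels relative to each vaccination:

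- Haematology: "2 ml taken at screening visit, at each vaccination visit and at 1, 7 and 28 days post each vaccination visit".
- Biochemistry: "4 ml taken at screening visit, at each vaccination visit, 7 and 28 days post each vaccination visit".
- Coagulation and fibrinogen: "3 ml taken at screening visit, each vaccination visit and 28 days post each vaccination visit".

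Group 2 is boosted at D28 (Synopsis), so 28 days after the boost is D56.

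In Table 2b, as it reads in the text copy, coagulation is marked at D56. Haematology and biochemistry are marked at D42 and are blank at D56. The stated volumes are 100 ml at D42 and 20 ml at D56, and the cumulative row ends at 599 ml. Section 7.4.3 tells site staff to "Collect blood tests and faeces as specified in the Schedule of Procedures".

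One primary endpoint is "Proportion of volunteers with Grade 3 or 4 unsolicited adverse events (AEs) through 28 days post final vaccination". Section 9.1.1 includes abnormal laboratory results among adverse events. Section 5.6 puts the Group 2 blood volume below 600 ml over the study period, and section 5.4 counts that period from enrolment.

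**The concern.** Section 7.3 and the schedule should describe the same draws, and the volume rows should follow from the schedule. For the 28-day post-boost visit they do not agree. The volume at D56 omits all three safety tubes, including the coagulation tube that the table itself marks there.

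Two things are at stake. The first is the stated blood volume, which section 5.6 uses to argue that sampling is harmless. The second is conditional. If haematology and biochemistry really are scheduled at D42 and not at D56, a symptomless Grade 3 or 4 abnormality of blood count, liver or renal function that arises after D42 has no scheduled test to reveal it before the primary endpoint window closes. On that reading no further blood count is scheduled until D140, although section 5.6 relies on the schedule for anaemia monitoring.

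**Working it through.** **Inputs.** Tube volumes come from the row labels of Tables 2a and 2b, and test times from section 7.3. HIV antibody needs its own 5 ml only when hepatitis serology is not drawn at the same visit (row label).

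**Step 1: the plan's own total.** The stated per-visit row adds up as printed: 14 + 140.5 + 4.5 + 8.5 + 16.5 + 4.5 + 128.5 + 100 + 20 + 22.5 + 139.5 = 599 ml.

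**Step 2: itemise each visit from the marks in the text copy.**

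| Visit | Itemised (ml) | Stated (ml) |
|---|---|---|
| Screen | 5+2+3+4 = 14 | 14 |
| D0 | 5+2+3+4+4+20+100+2.5 = 140.5 | 140.5 |
| D1 | 2+2.5 = 4.5 | 4.5 |
| D7 | 2+4+2.5 = 8.5 | 8.5 |
| D28 | 5+2+3+4+2.5 = 16.5 | 16.5 |
| D29 | 2+2.5 = 4.5 | 4.5 |
| D35 | 2+4+20+100+2.5 = 128.5 | 128.5 |
| D42 | 100+2+4 = 106 | 100 |
| D56 | 20+3 = 23 | 20 |
| D84 | 20+2.5 = 22.5 | 22.5 |
| D140 | 5+10+2+20+100+2.5 = 139.5 | 139.5 |

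D14 is a telephone visit with no blood. Only D42 and D56 fail.

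**Step 3: total by row counts, which does not depend on column position.** Haematology 9×2, coagulation 4×3, biochemistry 6×4, serology 4×5, HIV-RNA 10, HLA 4, fresh ELISpot 3×20, PBMC storage 4×100, epitope mapping 2×20, innate response 8×2.5:

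18 + 12 + 24 + 20 + 10 + 4 + 60 + 400 + 40 + 20 = 608 ml.

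608 − 599 = 9 ml (1.5%), and 9 = 2 + 4 + 3. From enrolment: 608 − 14 = 594 ml.

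**Step 4: compare mark counts with section 7.3.**

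- Biochemistry needs Screen, D0, D7, D28, D35, D56 (6). The row has 6 marks: five match and the sixth is at D42.
- Haematology needs Screen, D0, D1, D7, D28, D29, D35, D56 (8). The row has 9 marks: seven match, one is an additional D140 draw (confirmed by the 139.5 ml), and one is at D42.
- Coagulation needs Screen, D0, D28, D56 (4). The row has 4, all matching.

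**Step 5: two readings of the D42 marks.**

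- Reading A (source shows D42): volumes are short by 6 ml at D42 and 3 ml at D56. The interval from D42 to D56 is 14 nominal days. With ±3-day windows it is (56−3)−(42+3) = 8 to (56+3)−(42−3) = 20 days.
- Reading B (source shows D56): D42 is 100 ml as stated, and D56 is 20+2+4+3 = 29 ml, short by 9 ml. There is no monitoring gap.

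Both total 608 ml. If tests are done at both visits, the total is 608 + 6 = 614 ml, or 614 − 14 = 600 ml from enrolment.

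**Step 6: Group 1.** Table 2a itemises to 6×2 + 3×3 + 4×4 + 2×5 + 5 + 10 = 62 ml. The stated row gives 21+13+2+6+9+17 = 68 ml. Screening is listed as 21 ml for 14 ml of tests, and D0 as 13 ml for 14 ml.

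**The case against.** The strongest objection is that the D42 marks may be displaced in the text copy. Other marks plainly are. In Table 2b the boost and an HIV counselling mark fall under D29. In Table 2a the vaccination falls under D1, and the last coagulation mark falls under D112, although the stated D28 volume of 9 ml (2+4+3) needs it at D28. Reading B also leaves only one volume column wrong instead of two, and the mark counts fit section 7.3 once the D42 marks are read as D56. Against this, the visible displacements run to the right, whereas Reading B needs a shift to the left in two separate rows. Neither reading is established. A reader might infer that the plan omits the 28-day post-boost blood count and biochemistry. The documents do not support that as a firm statement.

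A second objection is that no clause ranks the schedule above section 7.3, which is itself an instruction to draw blood. That stands: sections 7.4 and 7.4.3 send staff to the table, but a site could follow 7.3. Also, D56 keeps its history, examination and adverse event review, and 7.3 allows discretionary bloods, so only symptomless laboratory events are exposed.

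A third concerns the blood limit. A reader might infer that 608 ml breaks the 600 ml statement in 5.6. Section 5.4 counts the study period from enrolment, which gives 594 ml, so the statement holds on that basis. It fails only if screening is counted, as the cumulative row does.

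Finally, it is tempting to conclude from the mark counts that the D42 marks should simply be moved. On Reading A that would delete a check 14 days after the boost and lengthen the stretch without haematology or biochemistry from 14 days (D42 to D56) to 21 (D35 to D56). The D140 blood count shows that the table can carry draws beyond 7.3, so a deliberate D42 draw cannot be excluded.

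None of this touches the volume discrepancy.

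**Conclusion.** The volume row of Table 2b is wrong wherever the D42 and D56 marks sit. It leaves no room for the safety bloods that section 7.3 requires at D56, and the marked tests exceed the stated total by 9 ml. This rests on the printed tube volumes and the number of marks in each row, not on column alignment. The size is small, and on its own it changes no endpoint, analysis or dose decision.

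The monitoring gap is conditional on the source table showing haematology and biochemistry at D42 only. In that case it covers 14 nominal days (8 to 20 with visit windows) of the 28-day post-boost window, in 10 volunteers, for symptomless laboratory abnormalities. If the marks are at D56 in the source, the gap is zero. The point is worth settling because the safety schedule of a first-in-human trial should agree with itself. The Group 1 volume error is clerical, and both of its totals are well under the 100 ml given in 5.6.

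**What to change.** 1. Check the haematology and biochemistry marks around D42 and D56 against the source table. Make sure both tests are marked at D56, using the draw already planned there. Drop a D42 draw only if the sponsor confirms it was not intended.
2. Correct the Table 2b volumes. D56 becomes 29 ml. With no D42 safety tests, D42 stays at 100 ml and the cumulative row reads 417, 446, 468.5 and 608 ml at D42, D56, D84 and D140 (stated: 417, 437, 459.5, 599).
3. If D42 tests are kept as well, D42 is 106 ml and the total is 614 ml. From enrolment that is 600 ml, which is no longer under 600, so the statement in 5.6 must be restated.
4. In either case, state in 5.6 whether the limit includes screening.
5. Minor: correct Table 2a to 14, 14, 2, 6, 9, 17 ml (Screen, D0, D1, D7, D28, D112); cumulative 14, 28, 30, 36, 45, 62 ml.

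The cost is a table correction and one clarifying sentence. No visit or venepuncture is added. Having the tests at D56 only adds nothing to the 608 ml itemised; keeping D42 as well adds 6 ml.

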7.4 Study visits

The study visits and procedures will be undertaken by one of the clinical trials team. The procedures to be included in each visit are documented in the Schedule of Procedures (Table 2). Each visit is assigned a time-point and a window period, within which the visit will be conducted.

